6.3 Screening Assessments

Screening may take place over several days. All screening assessments will be performed within 30 days prior to flortaucipir F 18 injection. Screening assessments will include:

- Informed consent for subject;
- Demographics (age, gender, years of education, race, ethnicity); weight;
- Medical history, concomitant medications;
- Vital Signs (pulse, respiration rate, supine blood pressure)
- A resting 12 lead ECG will be performed to assess the subject's cardiac status. If an ECG was performed within the last 12 months of the flortaucipir (¹⁸F) PET Imaging Visit and is available for review, the ECG does not need to be repeated.
- ApoE status, if available;
- Disease history (date/months since symptom onset, date/months since diagnosis, family history of relevant neurologic disease);
- Cognitive status interview, including MMSE;
- A physician will see the subject during the screening visit.
- For women of childbearing potential, a negative serum pregnancy test must be obtained at the screening visit

Weight will be displayed in kilograms (kg), height will be displayed in centimeters (cm). Weights and heights recorded in alternate units will be converted to the units being

displayed using standard conversion formulas. Body mass index (BMI) will be calculated as weight (kg) divided by height squared (cm²).

APOE4 Positive is any subject with at least one of their two APOE alleles as an E4 allele.

Each subject's age (years) will be calculated based on his/her date of informed consent and will be truncated to a whole number. Because only year of birth is collected, January 1 will be imputed for the month and day of birth. Age will be calculated as the number of months between the date of informed consent and the imputed birthdate, divided by 12. Age will be rounded to the nearest integer.

The MMSE (Folstein et al., 1975) is a brief instrument used to assess cognitive function in elderly subjects. The instrument is divided into 2 sections. The first section measures orientation, memory, and attention. The maximum score for the first section is 21. The second section tests the ability of the subject to name objects, follow verbal and written commands, write a sentence, and copy figures. The maximum score for the second section is 9. The range for the total MMSE score is 0 to 30, the sum of each correct answer, with higher scores indicating better cognition.

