8.1.2 Safety Population

The safety analysis population will include all eligible subjects who enroll in ¹⁸F-AV-1451-A23 (A23) and have received at least one dose of flortaucipir F 18 injection.

All demographic, baseline and safety endpoints will be using the safety population.

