8.4 Demographic and Other Baseline Characteristics

All baseline summaries will be based on the safety population.

Frequency distributions and summary statistics for demographic and baseline variables will be presented across all subjects. Key demographic and baseline characteristics to be summarized include: age, gender, race, ethnicity, height, weight, BMI, highest level of education, alcohol history, recreational drug use history, smoking history, MMSE, and ApoE Genetic testing.

All demographic and baseline characteristics data will be presented in listings.

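### SAP 6.3 tells the programmer both to truncate age and to round it, and defines BMI in kg/cm², which is 10,000 times too small

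*SAP*

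**What the plan says.** All the definitions are in SAP section 6.3, Screening Assessments.

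- **Birth date:** "Because only year of birth is collected, January 1 will be imputed for the month and day of birth".
- **Age formula:** "Age will be calculated as the number of months between the date of informed consent and the imputed birthdate, divided by 12".
- **Conversion to an integer, given twice:** age "will be truncated to a whole number", and, at the end of the same paragraph, "Age will be rounded to the nearest integer".
- **BMI:** kilograms over centimetres squared, with no conversion to metres. "Weights and heights recorded in alternate units will be converted" to the display units, which are kg and cm.

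SAP 8.4 lists "age, gender, race, ethnicity, height, weight, BMI" among the key baseline variables to be summarized, and it requires listings as well. SAP 8.1.2 fixes the analysis set: "All demographic, baseline and safety endpoints will be using the safety population". The protocol derives neither age nor BMI, and SAP 5.2 reports no change from the planned analyses, so no other text settles either definition.

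**The concern.** The two integer rules cannot be read as consecutive steps. Once either has been applied to months divided by 12, the result is a whole number and the other rule does nothing. The outcome therefore depends on which is applied first, and the SAP gives no order. Because every birthday is set to 1 January, the disagreement is systematic: it falls on subjects who consent in the second half of the year and always goes in the same direction. Two programmers working independently from this paragraph could produce different age tables, both plausible, and nothing in the output would show that something was wrong.

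The BMI definition has only one reading, but that reading is not kg/m². Followed literally, it puts a named baseline variable on a scale no reader would recognise.

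**Working it through.** The plan states no numerical age or BMI, so there is no figure to reproduce. The rules are applied directly.

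**Age: where the rules differ.** Inputs from SAP 6.3: birth on 1 January of the birth year; age = months to consent / 12. Illustrative values: birth year 1950, consent in 2018, whole months counted, halves rounded up. The SAP specifies neither of these last two conventions.

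| Consent month | Months / 12 | Truncated | Rounded |
|---|---|---|---|
| June | 821/12 = 68.42 | 68 | 68 |
| July | 822/12 = 68.50 | 68 | 69 |
| December | 827/12 = 68.92 | 68 | 69 |

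Truncation always gives consent year minus birth year. Rounding gives the same for January to June and one year more for July to December, which is 184 of 365 days, or 50.4%. If all of the approximately 500 planned subjects consented evenly over the year (an assumption), about 500 × 184/365 = 252 would be affected.

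Other conventions move only the edge of this window. Fractional months (days/30.4375) leave one to three days at the start of July in agreement and in some years put 1 January in disagreement. Half-to-even rounding brings July into agreement when the truncated age is even.

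**Age: size of the difference.** Let p be the share of subjects consenting in July to December. The rules differ by 1 year for that share and by 0 otherwise, so mean age differs by p. The documents give no consent dates; p is taken as 0.3 to 0.7.

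**Age: which rule is closer to the truth.** Let f be the birth date and c the consent date, each as a fraction of its year. Assume f is uniform over the year and c is uniform within each half-year. True decimal age is (consent year − birth year) + c − f.

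- Truncation error is f − c, with mean 0.25 − 0.5p and mean square 1/6.
- Rounding error is f − c, plus 1 if c ≥ 0.5, with mean 0.25 + 0.5p and mean square 1/6 + p/2.

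| p | Mean error, truncation | Mean error, rounding | Root mean square, truncation | Root mean square, rounding |
|---|---|---|---|---|
| 0.3 | +0.10 | +0.40 | 0.41 | 0.56 |
| 0.5 | 0.00 | +0.50 | 0.41 | 0.65 |
| 0.7 | −0.10 | +0.60 | 0.41 | 0.72 |

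Measured against completed years at p = 0.5, truncation averages +0.5 year and rounding +1.0 year. Truncation is nearer on either yardstick. Rounding also makes an error of two years possible: a subject consenting in the second half of the year whose birthday has not yet come is listed two years too old. At p = 0.5 this is 0.5 × 0.25 = 12.5% of subjects.

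**BMI.** Inputs: the SAP formula and an illustrative subject of 70 kg and 170 cm.

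- As written: 70/170² = 0.00242.
- In kg/m²: 70/1.70² = 24.22.
- Ratio: 100² = 10,000, whatever the subject's size.

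Over an assumed range of 45 to 130 kg and 150 to 190 cm, the written formula runs from 45/190² = 0.0012 to 130/150² = 0.0058. Every such value would print as 0.0 if BMI were shown to one decimal; the documents do not state the display precision.

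**The case against.** The strongest objection is that nothing of consequence depends on either variable. The objectives are to pre-screen by scan and to add to the safety database. SAP 7.1 summarizes everything as one group, SAP 7.2 treats covariate adjustment as not applicable for the primary analyses, and SAP 7.8 rules out subgroups. The age criterion in protocol 5.3.1 applies at consent, and no passage ties it to the derived age. The BMI formula is an evident unit slip that the quality control in SAP 9 would probably catch. All of this stands, and it is why the point ranks low.

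A second objection is that July to December is too exact a boundary, because the SAP defines neither the month count nor the treatment of ties. That is right about the edge: a few early July days, or July itself in some years. August to December is unaffected under every convention examined.

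Third, the 1 January imputation already puts derived age up to a year out, so the conflict adds an error of similar size. True, but the imputation is a disclosed limitation with one defined result, whereas the conflict leaves the result itself undefined.

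Finally, either rule alone would remove the contradiction, so preferring truncation is partly a matter of choice. The ranking does rest on assumed distributions of birth and consent dates. Within the range examined, however, truncation has the smaller error throughout.

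**Conclusion.** Both parts hold. As written, SAP 6.3 does not determine reported age for subjects consenting in about the second half of the year: there are two candidate values one year apart. Mean age moves by 0.3 to 0.7 year between the rules if 30% to 70% of subjects consent in July to December. That share is an assumption, since the documents give neither consent dates nor the size of the safety population. The BMI formula is wrong by a factor of exactly 10,000, with no assumption needed.

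Severity is low, because the effect is confined to the baseline tables and listings. Of the two, the age conflict deserves more attention, because both answers look reasonable and a check of the output would not expose it. It could also show at the upper age limit of 85 in protocol 5.3.1. An eligible 85-year-old can be listed as 86 through the imputation alone, and as 87 if rounding is applied. A reader could take that for an entry violation of the kind SAP 8.3 lists.

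**What to change.** Four small changes to the SAP, before programming:

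1. Keep truncation and delete the sentence "Age will be rounded to the nearest integer". Say that completed months are counted, so that age is always consent year minus birth year.
2. Define BMI as weight (kg) / [height (cm)/100]², in kg/m².
3. Footnote the demographic table and listing to say that age is derived from year of birth only and may exceed completed age by one year.
4. While correcting the formula, confirm that the eCRF records height. SAP 6.3 provides for converting it and SAP 8.4 summarizes it, but the screening lists (protocol 7.1.1, SAP 6.3) and the flow charts (protocol 11.2, SAP 6.1) name only weight.

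The cost is one sentence deleted, one clause and one footnote added, and one formula corrected. The protocol need not change, and no new data are needed if height is already collected.

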6.4 Efficacy Variables

6.4.1 Qualitative assessment for Flortaucipir and Diagnostic Performance

The flortaucipir scan image will be visually interpreted. The scans will be classified as either

- Not consistent with an AD pattern (τ AD-)
- AD pattern (τ AD+)
- AD pattern and likely to progress (τ AD++)

6.4.2 Quantitative assessment of images for Flortaucipir (SUVr based)

For the flortaucipir image, standard uptake value ratios (SUVr) will be calculated to estimate tau globally. SUVr will be calculated after the visual read and only on scans that were τ AD+ or τ AD++. For global assessment, a target region derived statistically with a Multiblock Barycentric Discriminant Analysis (MUBADA) method will be used.

6.4.3 Increased neocortical Flortaucipir activity

The hemisphere and region of increased neocortical flortaucipir activity will be identified.

The hemisphere will be classified as either left or right and the region is classified as

- Anterior Lateral Temporal
- Posterior Lateral Temporal
- Occipital
- Parietal
- Precuneus
- Frontal

6.5 Drug Concentration Measurements and Pharmacokinetic Parameters

No pharmacokinetic parameters or drug concentration measurements will be collected during this study.

6.6 Safety Assessments

6.6.1 Extent of Exposure and Compliance to Study Treatment

During the flortaucipir imaging session, subjects will receive a single IV bolus administration target dose of 370 MBq (10 mCi) of flortaucipir F 18 injection followed by a saline flush. At approximately 75 minutes following injection, a continuous 30-minute brain scan will begin. Exposure to study drug will be summarized using the total administered dose at the scan visit for flortaucipir F 18 injection.

6.6.2 Adverse Events

The investigator's verbatim term of adverse events will be mapped to system organ class (SOC) and preferred terms using the current version of the Medical Dictionary for Regulatory Activities (MedDRA).

Treatment-emergent AEs (TEAEs) are undesirable experiences, signs, or symptoms that begin or worsen in intensity or frequency at the time of or after the administration of study drug at the imaging visit, and prior to the end of observation windows defined as following: the TEAE window will be from injection of flortaucipir F 18 until 48 hours post flortaucipir F 18 injection. These will be recorded on the AE page of the electronic case report form (eCRF).

Serious AEs (SAEs) are events that result in one of the following outcomes or constitute one of the following events:

- Death
- Initial or prolonged hospitalization (other than that required by protocol; “social hospitalization” or any hospitalization for non-medical reasons does not constitute an SAE
- A life-threatening experience (that is, immediate risk of dying)
- Persistent or significant disability/incapacity
- Congenital anomaly/birth defect
- Considered significant by the investigator for any other reason

Important medical events that may not result in death, are life-threatening, or require hospitalization may be considered serious adverse drug events when, based upon appropriate medical judgment, they may jeopardize the patient and may require medical or surgical intervention to prevent one of the outcomes listed in this definition.

For the summarization of TEAEs by seriousness, events recorded with missing seriousness will be summarized as serious.

Investigators will be instructed to report their assessment of the potential relatedness of each AE to protocol procedure or study drug. The assessment of the relationship of an AE to the administration of the investigational product is a clinical decision based on all available information at the time of the completion of the eCRF. For the summarization of TEAEs by relationship to study drug or protocol procedure, events recorded with missing relationship will be summarized as Related.

In addition to assessing the relationship of the administration of the investigational product to AEs, an assessment is required of the severity of the event. The following classifications should be used:

Mild:

A mild AE is an AE, usually transient in nature and generally not interfering with normal activities.

Moderate:

A moderate AE is an AE that is sufficiently discomforting to interfere with normal activities.

Severe:

A severe AE is an AE that incapacitates the subject and prevents normal activities. Note that a severe event is not necessarily a serious event. Nor must a serious event necessarily be severe.

For the summarization of TEAEs by intensity, events recorded with missing intensity will be summarized as Severe.

6.6.3 Other Observations Related to Safety

6.6.3.1 Vital Signs

Vital signs (pulse rate, respiratory rate, and supine blood pressure) will be taken at the screening visit. Weight will be measured, lightly clothed during the imaging visit.

6.6.3.2 Electrocardiogram (ECG)

A resting 12-lead electrocardiogram will be recorded as part of the screening visit, unless an ECG was performed within twelve months of the flortaucipir PET Imaging Visit and is available for review.

6.7 Pharmacodynamics Parameters

No pharmacodynamics parameters will be collected during this study.

7 STATISTICAL METHODS

7.1 General Methodology

All values will be summarized as a single group, early symptomatic AD. Frequency distributions including counts and percentages will be reported for all categorical outcomes. Summary statistics including number of subjects [N], mean, standard deviation [SD], median, quartiles, minimum and maximum values will be presented for all continuous outcomes.

All statistical analyses will be performed using SAS® version 9.3 or higher. Patient listings of all data from the eCRF as well as any derived variables will be presented.

7.2 Adjustments for Covariates

Not applicable for the primary analyses.

7.3 Handling of Dropouts or Missing Data

Dropout subjects will not be replaced in this study. For situations with no rules for handling missing data, the default will be no imputation.

7.4 Interim Analyses and Data Monitoring

No interim analysis or data monitoring is planned for this study

7.5 Multi-center Studies and Pooling of Centers

This study will be conducted in approximately 15 centers. The data from all centers will be pooled. The pooled data will be analyzed and presented.

7.6 Multiple Comparisons/Multiplicity

No adjustment for multiplicity will be performed in this study.

7.7 Active-Control Studies Intended to Show Equivalence

Not applicable to this study.

7.8 Examination of Subgroups

No subgroup analysis will be performed.

8 STATISTICAL ANALYSIS

8.1 Analysis Populations

8.1.1 Enrolled Population

The enrolled population will consist of all subjects who signed informed consent and have data captured in the clinical database. Disposition information will be summarized using the enrolled population.

8.1.2 Safety Population

The safety analysis population will include all eligible subjects who enroll in ¹⁸F-AV-1451-A23 (A23) and have received at least one dose of flortaucipir F 18 injection.

All demographic, baseline and safety endpoints will be using the safety population.

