#### **8.1.1. Population for Analysis**

The safety analysis population will include all eligible patients who enroll in F-AV-1451-A23 (A23) and have received at least one dose of flortaucipir F 18 injection. Efficacy analysis population will include all subjects in safety population, and with a valid flortaucipir F 18 scan assessment (quantitative and/or qualitative).

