8.1.3 Efficacy Population

Efficacy analysis population will include all subjects in safety population, with a valid flortaucipir scan assessment [SUVr (quantitative) and/or visual reads (qualitative)].

For flortaucipir SUVr related analyses, any scans deemed to be unquantifiable due to technical reasons will be excluded from analyses.

All analyses involving imaging outcomes will be based on the efficacy population.

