8.3 Protocol Deviations/Violations

Subjects who entered the study even though they did not satisfy one or more of the inclusion/exclusion criteria will be listed. Deviations/violations from the protocol will be documented, the Avid/contract research organization (CRO) monitor will then be informed and a course of action will be agreed upon.

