8.8 Concomitant Therapy

A current version of the World Health Organization (WHO) Drug Dictionary will be used to classify medications by preferred term and WHO Anatomical Therapeutic Chemical (ATC) classification of ingredients. ATC classification level 3 will be used. If level 3 is missing, then level 2 will be used. If level 2 is missing, then level 1 will be used.

All concomitant medications data will be presented in listings for the safety population.

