8.11 Analysis of Safety

8.11.1 Extent of Exposure and Compliance to Study Treatment

The total dose administered (MBq) of Flortaucipir F 18 will be summarized using descriptive statistics. All exposure data captured on the CRF will be presented in listings for the safety population.

Because this is a study with only one bolus of study medication per imaging visit, compliance will not be summarized.

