8.11.2 Adverse Events

TEAEs will be summarized by descending frequency, then alphabetically by SOC and preferred term. A subject will only be counted once per SOC and once per preferred term. Subject counts and percentages will be presented for the following summaries:

1. All TEAEs by system organ class (SOC) and preferred term;
2. All TEAEs by preferred term (in order of descending frequency);
3. All TEAEs by relationship to study drug, SOC, and preferred term;
4. All TEAEs by relationship to protocol procedure, SOC and preferred term;
5. All TEAEs by severity, SOC and preferred term
6. All Serious TEAEs by system organ class (SOC) and preferred term;
7. All TEAE leading to study termination by system organ class (SOC) and preferred term

For the summary of TEAEs by severity, if a subject has multiple events occurring in the same SOC or same preferred term, the event with the highest severity will be counted.

TEAEs by relationship to study drug and protocol procedure will be summarized as Related vs. Not Related. If a subject has multiple events occurring in the same SOC or same preferred term, the related event will be summarized.

All AE will be presented in the listings.

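### The safety population is limited to eligible dosed subjects, with eligible undefined and no all-dosed set, so injected entry-criteria violators can drop out of the safety summaries

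*SAP*

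**What the plan says.** SAP 8.1.2: "The safety analysis population will include all eligible subjects who enroll in" the study and have had at least one injection. Protocol 8.1.1 matches it: "The safety analysis population will include all eligible patients who enroll in" the study, again with the dosing condition. Membership therefore has two tests, eligibility and dosing.

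SAP 8.1.2 then ties the analyses to this set: "All demographic, baseline and safety endpoints will be using the safety population". SAP 8.1.3 builds the imaging set from it: "Efficacy analysis population will include all subjects in safety population, with a valid flortaucipir scan assessment". The only other set is the enrolled population (SAP 8.1.1), which is defined by consent and data in the database and is used for disposition.

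SAP 8.3 foresees breaches: "Subjects who entered the study even though they did not satisfy one or more of the inclusion/exclusion criteria will be listed". It does not say whether those subjects belong to the safety population.

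Some listings carry the same restriction. SAP 8.11.1: "All exposure data captured on the CRF will be presented in listings for the safety population". SAP 8.8: "All concomitant medications data will be presented in listings for the safety population". The adverse event listing has no stated limit (SAP 8.11.2): "All AE will be presented in the listings". SAP 7.1 promises listings of all eCRF data.

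**The concern.** Safety information comes from exposure, and a subject who was injected is exposed whether or not every entry criterion was met. A population that also requires eligibility can remove exposed subjects from both the numerator and the denominator of the safety tables. The only secondary objective (Protocol 2, SAP 3) is to add to the safety database, so those tables are what the study delivers on that objective.

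Collection and analysis also do not match. Protocol 7.7.4 collects serious adverse events for 48 hours after dosing with no eligibility condition. An event in a violator could therefore appear in the adverse event listing while that subject's dose and concomitant medication are missing from theirs.

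The direction of any bias cannot be read from the documents. Some entry criteria bear on safety (QTcF limit, QT-prolonging drugs, unstable illness). Many do not (MMSE range, MRI contraindication).

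**Working it through.** **Step 1: what eligible can mean.** The plan gives no analysis definition, so the uses of the word have to be compared.

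- *Reading 1, entry criteria met.* Protocol 5.3.2 calls a patient with any listed exclusion not eligible to enroll. This is the ordinary sense, and under it a dosed violator is outside the safety population.
- *Reading 2, cleared to proceed.* SAP 4.1 speaks of subjects judged eligible at screening who go on to the scan. Under it, a subject whose breach is found later stays in.

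Reading 1 is also hard to apply. Exclusions 13, 25 and 31 are timed to randomization, and this single-group study has none.

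**Step 2: what a dosed violator loses under reading 1.**

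| Output | Included? | Source |
|---|---|---|
| Baseline, exposure, TEAE, vital sign and ECG summaries | No | SAP 8.1.2 |
| Imaging summaries | No | SAP 8.1.3 |
| Exposure, concomitant medication, medical history and pregnancy test listings | No, in conflict with SAP 7.1 | SAP 8.11.1, 8.8, 8.9, 8.7 |
| Adverse event listing | Probably | SAP 8.11.2 |
| Deviation listing, disposition | Yes | SAP 8.3, 8.1.1, 8.2 |

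The gap is in the summary tables and restricted listings. Event collection is not affected.

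**Step 3: size under reading 1.** The plan states no figure to reproduce. About 500 subjects are planned (SAP 4.5); assume that all are dosed. Two further quantities are assumptions:

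- *q*: the fraction of dosed subjects who are ineligible, taken as 2%, 5% and 10%.
- *k*: their event risk relative to eligible subjects, taken as 0.5, 1, 2 and 5.

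If eligible subjects have rate *p*, the tables report *p*, while the all-dosed rate is *p*[(1 − q) + qk]. Hence

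reported ÷ all-dosed = 1 / [(1 − q) + qk].

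For example, q = 0.10 and k = 2 give 1/1.10 = 0.909, which is 9.09% too low.

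| | q = 2% | q = 5% | q = 10% |
|---|---|---|---|
| Exposed subjects missing (500q) | 10 | 25 | 50 |
| k = 0.5 | 1.01% too high | 2.56% too high | 5.26% too high |
| k = 1 | no change | no change | no change |
| k = 2 | 1.96% too low | 4.76% too low | 9.09% too low |
| k = 5 | 7.41% too low | 16.67% too low | 28.57% too low |

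These are relative errors. In absolute terms, with an assumed 5% TEAE rate in eligible subjects, the tables show 5.0%. The all-dosed rate would be 5.10%, 5.25% and 5.50% for k = 2, and 5.40%, 6.00% and 7.00% for k = 5.

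**Step 4: precision.** The one-sided 95% upper bound for an event never seen is 1 − 0.05^(1/n): 0.597% at n = 500, 0.610% at 490, 0.629% at 475 and 0.664% at 450. The loss of precision is small.

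**The case against.** The strongest reply is that reading 2 may be what the sponsor means, in which case the safety population is in practice everyone injected. SAP 8.10.1 gives some support. It splits visual reads by subject eligibility within the efficacy population, which is a subset of the safety population. If eligibility there means the entry criteria, reading 1 leaves the ineligible group empty by construction. SAP 8.3 lists violators and does not order their removal. This shows that reading 2 is possible, but it does not settle the matter: the split could refer to eligibility for a trial such as AACG, which would be a third sense. The rule as written still makes eligibility a condition, and its ordinary meaning excludes violators.

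A second reply is that little safety content is at risk. Vital signs and ECG are taken only at screening, and the ECG may be up to 12 months old, so the post-injection content is essentially TEAEs and administered dose. Adverse events are probably listed in any case. That is correct, and it limits the loss to the tables and restricted listings.

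A third reply is that q, k and the 5% rate are all assumed, and that 28.57% is the extreme corner of the grid. That also stands. Nothing in the documents supports a particular k, and Protocol 1 describes a low incidence of mild, transient events. The count of missing exposed subjects, however, does not depend on k.

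**Conclusion.** The concern holds. The rule followed literally can drop injected subjects from the tables that serve the only secondary objective, and the text lets two programmers build different safety populations. This is a fault in a stated rule and should be fixed.

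The size is conditional on reading 1. For q of 2% to 10%, 10 to 50 exposed subjects are missing. The relative error in a reported rate runs from about 5% too high (k = 0.5) through none (k = 1) to 9% too low (k = 2), and to 29% too low only at q = 10% with k = 5. Ineligible dosing may turn out to be zero, and then no result changes. The direction of bias is unknown, precision is hardly affected, and event collection is intact.

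**What to change.** In Protocol 8.1.1 and SAP 8.1.2, delete the word eligible and define the safety population as all subjects who received at least one dose of flortaucipir F 18 injection, regardless of whether entry criteria were met. Flag entry-criteria violators in the listings. SAP 8.1.3 can keep its wording and will then include flagged subjects with a valid scan. If the sponsor wants them out of the imaging tables, SAP 8.1.3 should say so directly, and the safety population should not be used for that purpose.

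The cost is a short wording change in two places and one flag variable, which the SAP 8.3 listing needs anyway. No new data are collected. The Protocol edit may have to go through the IRB/IEC, whose approval of the protocol Protocol 10.1 requires. If the SAP is changed first, record the difference in SAP 5.2, which now reports no changes from the Protocol analyses. Reported event rates may move in either direction.
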